4.1.5 Intravitreal Injection Technique and Sham Injection

IVT injections must be carried out according to medical standards and applicable guidelines by a qualified physician experienced in administering IVT injections. In general, adequate anaesthesia and asepsis, including topical broad-spectrum microbicide (e.g. povidone iodine applied to the periocular skin, eyelid and ocular surface) have to be ensured. Surgical hand disinfection, sterile gloves, a sterile drape, and a sterile eyelid speculum (or equivalent) to be used in accordance with local standards and regulations.

Part B is designed double-masked and personnel of the trial site are masked. Therefore, in Part B, an unmasked injector with no other involvement in the trial will administer IVT/sham injections.

For a sham injection, all pre- and post-injection procedures are identical compared to IVT injections. For a sham injection, the hub of a syringe without a needle is pressed against the conjunctival surface to simulate the force of an actual injection. For sham aqueous sampling, all procedures are identical to aqueous sampling, the hub of a syringe without a needle is pressed gently against the corneal surface to simulate aqueous sampling.

Use of antibiotics in the pre-, peri-, or post-injection period is at investigator's discretion.

After administration of BI 765128, subjects will be monitored according to standard local practice. In this minimum post-dose observation period, systemic and ocular conditions will be monitored according to local practice for such procedures.

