6.2.2 Treatment period(s)

For Part A, masking is not required for the IVT injection preparation or administration. For Part B, IVT injection will be prepared by the unmasked pharmacist/qualified person (Section 4.1.6). In addition, an unmasked injector (Section 4.1.6) with no other involvement in the trial will administer either active or sham injection according to the treatment assigned by IRT. IVT injections must be carried out according to medical standards and applicable guidelines by a qualified physician experienced in administering IVT injections and will be done as part of drug administration visit procedures (Visit 2 for Part A and Visits 2, 3 and 4 for Part B) after the other ophthalmologic assessments in the [Flow Chart I](#) and [Flow Chart II](#) have been performed (please see Section 4.1 for details).

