6.6 HANDLING OF MISSING DATA AND OUTLIERS

Handling of missing data and outliers will be performed as described in the CTP, Section 7.4.

Section 7.4 of the CTP:

Safety

Missing baseline laboratory values will be imputed by the respective values from the screening visit. No other imputations will be performed on missing data although every effort will be made to obtain complete information on all AEs, with particular emphasis on potential DLEs.

[REDACTED]

[REDACTED]

[REDACTED]

Efficacy

All data will be analyzed and presented without any form of imputation.

Missing time at unscheduled ocular assessments performed on the day of administration are regarded as on treatment. The missing time will be imputed and set to 23:59 at the day of administration.

Missing or incomplete AE dates are imputed according to BI standards (see BI-KMED-BDS-HTG-0035) (3).

Missing data and outliers of PK data are handled according to BI standards (see BI-KMED-TMCP-HTG-0025 (4) and BI-KMED-TMCP-MAN-0014 (5)).

ECG analysis

If single cardiac cycles of an ECG (out of the generally four) are missing, the arithmetic mean for this single ECG will be computed with the reduced (1, 2 or 3) number of cardiac cycles.

If replicate ECG recordings are missing, the arithmetic means per time point will be computed with the reduced number (1 or 2) of recordings.

For the classification of the on-treatment QTc/QT intervals into “no new onset” / “new onset” categories, the handling of missing values is described in Additional [Section 10.1.2](#).

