6.7 BASELINE, TIME WINDOWS AND CALCULATED VISITS

Section 5.1 of the CTP:

For the endpoints, baseline is defined as the value at Visit 2; if not measured at Visit 2 then baseline is the value at Visit 1.

Baseline is defined as the last measurement before first administration of trial medication.

Section 6.1 of the CTP:

The acceptable time windows for visits are given in the CTP Flow Charts. For planned individual serum concentration sampling times, refer to CTP appendix 10.1.

Analysis of AE data, potentially clinically significant abnormal laboratory values, concomitant medication or non-drug therapies, as well as use of rescue therapy will not be based on visits. Therefore, no assignment to time windows will be necessary for such data.

All other safety and efficacy measurements will be assigned to visits based on extended time windows around the planned visit dates, defined relative to the day of first trial treatment (which is scheduled for Visit 2). These extended time windows are defined in [Table 6.7: 1](#) to [Table 6.7: 5](#).

Only one observation per time window will be selected for statistical analysis at a particular visit – the value which is closest to the protocol planned visit day will be selected, except for safety lab and ████ where the worst scenario is chosen (i.e. for IOP the highest value will be taken). If there are two observations which have the same difference in days to the planned day, the later value will be selected. If there is more than one IOP measurement being the worst value within a time window, the value collected closer to the planned day will be selected.

Proprietary confidential information © 2023 Boehringer Ingelheim International GmbH or one or more of its affiliated companies.

Table 6.7: 1 Time window assignment of efficacy, safety lab, ████, vital signs and weight measurements to visits for statistical analysis of the SRD Part

Visit (CTP)	Week	Visit label (analysis)	Planned Day	Time window [days]		
				Window per CTP	Start (extended)	End (extended)
V2	Baseline	Baseline	1	± 0	NA	1
V3*		Day 4 (FU)	4	± 1	2	6
V4*	Week 1	Day 8 (FU)	8	± 2	7	11
V5	Week 2	Day 15 (FU)	15	± 2	12	22
V6	Week 4	Day 29 (FU)	29	± 3	23	43
V7	Week 8	Day 57 (FU)	57	± 7	44	78
V8	Week 14/EOS	Day 99 (EOS)	99	± 7	79	End of Trial visit date

* Safety lab is not scheduled for Day 4. Consequently, the time window for Day 8 is [2, 11], the other time windows remain the same.

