Table 6.7: 2 Time window assignment of 12 lead ECG measurements to visits for statistical analysis of the SRD Part

Visit (CTP)	Week	Visit label (analysis)	Planned Day	Time window [days]		
				Window per CTP	Start (extended)	End (extended)
V2	Baseline	Baseline	1	± 0	NA	1
V3		Day 4 (FU)	4	± 1	2	16
V6	Week 4	Day 29 (FU)	29	± 3	17	43
V7	Week 8	Day 57 (FU)	57	± 7	44	78
V8	Week 14/EOS	Day 99 (EOS)	99	± 7	79	End of Trial visit date

Days are counted relative to the day of first treatment, which is defined as Day 1.

Table 6.7: 3 Time window assignment of efficacy, safety lab, ████ and vital signs measurements to visits for statistical analysis of the MD Part

Visit (CTP)	Week	Visit label (analysis)	Planned Day	Time window [days]		
				Window per CTP	Start (extended)	End (extended)
V2	Baseline	Baseline	1	± 0	NA	1
V3	Week 4	Day 29	29	± 3	2	43
V4	Week 8	Day 57	57	± 3	44	71

Visit (CTP)	Week	Visit label (analysis)	Planned Day	Time window [days]		
				Window per CTP	Start (extended)	End (extended)
V5	Week 12	Day 85 (FU)	85	± 7	72	99
V6	Week 16	Day 113 (FU)	113	± 7	100	127
V7	Week 20/EOS	Day 141 (EOS)	141	± 7	128	End of Trial visit date

Table 6.7: 4 Time window assignment of 12 lead ECG measurements to visits for statistical analysis of the MD Part

Visit (CTP)	Week	Visit label (analysis)	Planned Day	Time window [days]		
				Window per CTP	Start (extended)	End (extended)
V2	Baseline	Baseline	1	± 0	NA	1
V3	Week 4	Day 29	29	± 3	2	43
V4	Week 8	Day 57	57	± 3	44	71
V5	Week 12	Day 85 (FU)	85	± 7	72	End of Trial visit date

Days are counted relative to the day of first treatment, which is defined as Day 1.

Table 6.7: 5 Time window assignment of physical examination measurements (weight) to visits for statistical analysis of the MD Part

Visit (CTP)	Week	Visit label (analysis)	Planned Day	Time window [days]		
				Window per CTP	Start (extended)	End (extended)
V2	Baseline	Baseline	-28 to -3	NA	NA	1
V5	Week 12	Day 85 (FU)	85	± 7	2	End of Trial visit date

Days are counted relative to the day of first treatment, which is defined as Day 1.

Section 5.2.5.1 of the CTP:

Central ECG lab evaluation will be performed for all ECGs indicated in the CTP Flow Chart I and CTP Flow Chart II. For all ECGs this will include the intervals RR, PR, QRS and QT measured semi-automatically. The screening ECGs will be checked for abnormalities.

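### The SAP's visit rules can replace the scheduled pre-injection eye reading with a post-injection one at Part B Visits 3 and 4, yet give the same kind of reading on Day 1 no post-baseline visit

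*SAP*

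**What the plan says.** **Order on dosing days.** Protocol 6.2.2 places the injection (Visit 2 in Part A; Visits 2, 3 and 4 in Part B) "after the other ophthalmologic assessments in the" flow charts, so scheduled BCVA, imaging and IOP are pre-injection values. Afterwards, under Protocol 4.1.5, "subjects will be monitored according to standard local practice". The visible text schedules no post-injection eye measurement.

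**Unscheduled same-day readings.** SAP 6.6 has a rule for unscheduled ocular assessments on an administration day that lack a clock time. They count as on treatment: "The missing time will be imputed and set to 23:59 at the day of administration".

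**Choice of one value per visit.** SAP 6.7 takes the reading closest to the planned day. For ties, "If there are two observations which have the same difference in days to the planned day, the later value will be selected". Safety laboratory data and one blacked-out parameter are exempt and use the worst case, "i.e. for IOP the highest value will be taken".

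**Baseline and windows.** "Baseline is defined as the last measurement before first administration of trial medication". In SAP Tables 6.7: 1 and 6.7: 3 the Baseline window ends on Day 1. The next window opens on Day 2: Days 2 to 6 for the Day 4 visit in Part A, and Days 2 to 43 for Visit 3 in Part B. Part B Visit 4 covers Days 44 to 71.

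**The concern.** A pressure or acuity reading taken shortly after an intravitreal injection measures something different from a reading taken four weeks after the previous one. The SAP foresees both kinds on the same calendar day, but its visit rules work in whole days and do not separate them. Two consequences follow.

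- **Doses are treated differently.** A post-injection reading can become the visit value after doses 2 and 3 but cannot appear in any by-visit summary after dose 1. In a first-in-human safety trial, such a table could suggest that pressure rises begin only with repeat dosing. In Part A, where Day 1 is the only dose, by-visit summaries cannot show the acute period at all.
- **Arms can be treated differently for IOP.** Sham is a needleless hub pressed on the conjunctiva (Protocol 4.1.5). A rise caused by injected volume can occur only in the active arm, and the highest-value rule then picks it up there.

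**Working it through.** The plan states no figure on this point, so the check applies the rules and then sizes the effect under stated assumptions.

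**Step 1: apply the SAP 6.7 rules to example IOP readings (invented values, mmHg).**

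| Day | Pre-injection | Post-injection | Value used |
|---|---|---|---|
| 1 | 15 | 32 | Baseline 15; the 32 has no visit |
| 29 | 15 | 30 | Visit 3 = 30 |
| 57 | 16 | 28 (untimed, set to 23:59) | Visit 4 = 28 |

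Reported changes from baseline are 30 − 15 = 15 and 28 − 15 = 13. The scheduled readings would give 15 − 15 = 0 and 16 − 15 = 1. The Day 1 rise of 32 − 15 = 17 enters no by-visit summary.

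If Day 29 reads 17 before and 14 after, the IOP rule keeps 17. A parameter under the closest-day rule would take the later reading, because two same-day readings are equally far from the planned day. This holds even if the visit is not exactly on Day 29 or 57. An untimed unscheduled reading becomes the later one through the 23:59 rule.

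**Step 2: size of the IOP effect at Visit 3 or 4.** Assumptions:

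- a share *f* of subjects in each arm has a recorded post-injection reading;
- the mean rise is *R* after active and 0 after sham;
- each reading has an independent within-eye SD of 2 mmHg.

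With θ = 2√2 = 2.83, the expected maximum of the two readings, relative to the pre-injection mean, is

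M(R) = R·Φ(R/θ) + θ·φ(R/θ).

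This gives M(0) = 1.13, M(5) = 5.04 and M(10) = 10.00. The active-minus-sham shift is f × [M(R) − M(0)]:

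| f | R = 0 | R = 5 | R = 10 |
|---|---|---|---|
| 0 | 0 | 0 | 0 |
| 25% | 0 | 0.25 × 3.91 = 0.98 | 0.25 × 8.87 = 2.22 |
| 50% | 0 | 0.50 × 3.91 = 1.96 | 0.50 × 8.87 = 4.44 |
| 100% | 0 | 3.9 | 8.9 |

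A simulation with 400,000 draws per arm agrees to about 0.01 mmHg. Sham also moves up, by f × 1.13 (0.28 at 25%, 1.13 at 100%), because the higher of two readings is taken.

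**Step 3: does it reach the BCVA endpoint?** SAP 7.5.2 fits treatment and baseline effects separately by visit with an unstructured covariance. With complete data this equals a separate regression at each visit. In one simulated 20:10 data set, each active subject had a one-half chance of a 10-letter drop imposed at Visits 3 and 4. The treatment difference moved from −2.007 to −8.472 at Visit 3 and from −0.355 to −6.821 at Visit 4. At Visits 5, 6 and 7 it did not move (0.224, 0.557 and −1.753 both ways).

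**The case against.** Several objections have force.

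- **The effect is conditional.** No post-injection measurement is scheduled in the visible text, and nothing suggests that ETDRS acuity is repeated after an injection. This stands: with no such records, nothing changes. But SAP 6.6 would not need a rule for these readings unless the sponsor expected some.
- **The tie rule does not govern IOP.** Correct. A post-injection IOP is used only when it is the highest, which is a deliberate worst-case choice for safety. That justifies keeping the rule, but not applying it to the acute period after doses 2 and 3 while leaving out dose 1.
- **Baseline is protected.** A reader of the window tables might infer that a Day 1 spike could become Baseline, since that window runs through Day 1. The SAP's definition of Baseline as a pre-dose value, together with the on-treatment status of untimed unscheduled readings, excludes this.
- **First-dose rises are not lost from the trial.** Individual values are listed (SAP 7) and AEs are not windowed (SAP 6.7). Clinically significant worsening is reported as an AE (Protocol 5.1), and IOP persistently above 30 mmHg for 3 days is a DLE and an AESI. This stands. What is missing is the by-visit summary of rises that are brief or not judged clinically significant.
- **The IOP output cannot be confirmed.** IOP is not a primary or secondary endpoint, and the section on further endpoints is not visible. Still, a rule for choosing one IOP value per visit implies a by-visit summary.

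**Conclusion.** The inconsistency is in the SAP's own rules and should be corrected. Its effect is limited to by-visit summaries, and to the Visit 3 and 4 terms of the models if post-injection readings of the modelled endpoints are recorded. For IOP, the rule-induced difference between arms at Visits 3 and 4 is zero without recorded post-injection readings. It is about 1 to 4 mmHg with readings in 25 to 50% of subjects and a mean rise of 5 to 10 mmHg. Those shares and rises, the 2 mmHg SD and equal recording in both arms are assumptions; the documents give no figures for them.

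A reader might also infer that BCVA is distorted by arm. The documents do not support that: the procedures around the injection are the same for sham and active (Protocol 4.1.5), so dilation or anaesthesia would affect both arms. Nor are the secondary endpoint visits affected directly. FAZ is assessed at Visits 5 to 7 and BCVA at Visit 7, none of them injection days. Values at Visits 3 and 4 could influence those estimates only through the modelling of missing data.

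**What to change.** In SAP 6.7:

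1. State that on administration days the visit value is the scheduled pre-injection measurement.
2. Assign every same-day post-injection ocular reading, including those on Day 1 and those set to 23:59, to a separate post-injection time point for each dose, in both parts.
3. Summarise the highest IOP at that time point, by arm in Part B and by dose group in Part A.
4. Keep the highest-IOP rule for all other readings.

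The worst-case intent is preserved, the three Part B doses become comparable, and same-day post-injection readings no longer create an arm difference in the Visit 3 and 4 values. The cost is SAP wording, one derived flag and one extra summary table. No new data are needed.

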7. PLANNED ANALYSIS

If not stated otherwise, all outputs will be displayed separately by study part.

Safety analysis (refer to [Section 7.8](#)) will be performed by [REDACTED] and will be presented in Sections 15.1 to 15.4 of the CTR and in Appendix 16.2 and 16.1.13.1.

Efficacy analysis of ophthalmological endpoints will be performed by the [REDACTED] and will be presented in Section 15.2 of the CTR and in Appendices 16.1.13.1.7 and 16.2.6.

[REDACTED]

No inferential statistical interim analysis was planned. A Bayesian logistic regression model (BLRM) analysis was performed after each dose group of trial part A to guide dose escalation in this study. The prior specified in the CTP Section 7.1 was used in all BLRM evaluations.

The data of the last screening attempt of re-screened patients will be considered. In case the last screening attempt of re-screened patients is missing this value will be imputed with the previous screening value.

The format of the listings and tables will follow the BI standards (see BI-KMED-BDS-HTG-0045 (6)) with the exception of those generated for PK-calculations following BI standards for PK/PD analysis (7).

The individual values of all subjects will be listed, sorted by treatment group, subject number and visit. The listings will be included in Appendix 16.2 of the CTR.

For end-of-text tables, the set of summary statistics for non-PK parameters is:

N	number non-missing observations
Mean	arithmetic mean
SD	standard deviation
Min	minimum
Median	median
Max	maximum

For analyte concentrations and PK parameters, the following descriptive statistics will additionally be calculated:

Tabulations of frequencies for categorical data will include all possible categories available in the CRF and will display the number of observations in a category, as well as the percentage (%). Percentages will be rounded to one decimal place and will be based on all subjects in the respective subject set whether they have non-missing values or not. The category 'missing' will be displayed only if there are actually missing values.

Units of variables should be given in the titles or column/row descriptors in brackets (e.g. (mg)).

7.1 DEMOGRAPHIC AND OTHER BASELINE CHARACTERISTICS

Only descriptive statistics are planned for this section of the report, based on the TS. The data will be summarised by treatment group and in total.

7.2 CONCOMITANT DISEASES AND MEDICATION

Frequency tables are planned for this section of the report, based on the TS.

Concomitant diseases will be coded using the coding system of the Medical Dictionary for Drug Regulatory Activities (MedDRA). Medications will be coded using the World Health Organization Drug Dictionary (WHO-DD). The coding version number will be displayed as a footnote in the respective output. If a concomitant medication has multiple Anatomical Therapeutic Chemical (ATC) codes, it is presented with all ATC codes.

The diagnoses and medications will be listed. Subjects without any concomitant diagnoses or concomitant therapies will be marked with a “No” in the respective column.

An additional table/listing will be provided for previous ophthalmic interventional therapies. Separate tables will be provided for concomitant medication before start of treatment and with new onset after start of treatment.

The relevance of the concomitant therapies to the evaluation of PK and efficacy endpoints will be decided no later than at the RPM.

7.3 TREATMENT COMPLIANCE

Section 4.3 of the CTP: *Compliance will be assured by administration of all trial medication in the trial centre under supervision of the investigating physician or a designee. The measured serum concentrations and urinary excretion of trial medication will provide additional confirmation of compliance.*

It is not intended to list the compliance separately. Any deviations from complete intake will be addressed in the RPM (cf. TSAP [Section 6.2](#)) and described in the CTR.

7.4 PRIMARY OBJECTIVE ANALYSIS

7.4.1 Main analysis

SRD part:

The primary endpoint ‘number of subjects with DLEs from drug administration till day 7’ will be analysed descriptively (see [Section 7.8](#) for details).

MD part:

Refer to TSAP [Section 7.8](#) for a description of the analysis of the primary endpoint (treatment-emergent drug-related AEs).

7.5 SECONDARY OBJECTIVE ANALYSIS

7.5.1 Key secondary objective analysis

This section is not applicable as no key secondary endpoint has been specified in the protocol.

7.5.2 Secondary objective analysis

Section 7.3.3 of the CTP:

The secondary endpoints (refer to [Section 5.2.2](#)) will be summarized by means of descriptive statistics (at least n, mean, standard deviation, median, minimum and maximum) for continuous variables or frequency tables for categorical variables. (...)

Analyses regarding safety and efficacy will be performed on the TS.

Model-based analyses will be performed for all ophthalmological efficacy endpoints of the MD part that were defined as secondary endpoints, i.e. FAZ area and BCVA. These analyses will only be done for the study eye and not for the fellow eye.

The change from baseline in the respective secondary endpoint will be analysed via a restricted maximum likelihood (REML) based approach using a mixed model with repeated measurements (MMRM).

The model will include the fixed, categorical effects of treatment at each visit and the fixed continuous effects of baseline at each visit. Visit will be treated as the repeated measure with an unstructured covariance structure used to model the within-patient measurements.

The statistical model will be as follows

$$y_{ijk} = \beta_j S_i + \tau_{jk} + e_{ij}$$

$$e_{ij} \sim N_Z(\mathbf{0}, \Sigma).$$

y_{ijk} = response variable (as change from baseline) for subject i at visit j receiving treatment k ,

S_i = the baseline measurement of subject i , $i=1,2,\dots$

β_j = coefficient of baseline effect at visit j

τ_{jk} = the effect of treatment k at visit j , $j=1,\dots,Z$ and $k = 1, \dots, Y$,

e_{ij} = the random error associated with the j^{th} visit of the i^{th} subject. Errors are independent between subjects.

Σ = an unstructured covariance matrix

The Kenward-Roger approximation will be used to estimate denominator degrees of freedom and adjust standard errors. Least-squares means per treatment and for the treatment difference will be provided by time point, and in addition corresponding two-sided 95% confidence intervals and p-values will be presented.

The following SAS code can be used to fit the model:

```
PROC MIXED DATA=indata CL METHOD=REML;
CLASS subject treat visit;
MODEL endpoint = baseline treat visit treat*visit baseline*visit/ DDFM=KR
CL
ALPHA=0.1;
REPEATED visit / SUBJECT=subject TYPE=UN;
LSMEANS treat*visit/ DIFF CL ALPHA=0.1 SLICE=visit;
RUN;
```

In the event of non-convergence, the following methods will be attempted (in order) to overcome it:

1. Add the 'singular=1e-10' option in the model statement – This raises the threshold at which columns are declared linearly dependent (from typically 1e-12).

Proprietary confidential information © 2023 Boehringer Ingelheim International GmbH or one or more of its affiliated companies.

2. Set 'maxiter=100' in the Proc Mixed statement – This increases the number of convergence iterations used from a default of 50.
3. Set 'scoring=4' to specify use of the Fisher scoring algorithm in the first 4 iterations.
4. Include the statement 'performance nothread' – this removes multi-threading from the calculations.

Should none of the previous methods work, the covariance matrix will be changed from unstructured to Toeplitz with heterogeneous variances (TOEPH). Should this also not converge, a standard Toeplitz matrix (TOEP) will be fitted. Finally, if convergence still does not occur, then an order-1 autoregressive matrix (AR(1)) will be fitted.

[figure not shown]
Furthermore, for the ophthalmological secondary endpoints, time profiles of mean (\pm SD) changes from baseline by treatment group as well as individual time profiles (absolute values and changes from baseline) per treatment group will be provided for the study eye / fellow eye. For the secondary endpoint FAZ area, these figures will be presented for absolute and percent changes whereas plots of the other secondary endpoint BCVA will only comprise absolute changes.

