4.1.3 Method of assigning subjects to treatment groups

After the assessment of all in- and exclusion criteria, subjects will be enrolled into the Part A and Part B. Recruitment in the trial will start with the lowest dose group of Part A. Part B will recruit subjects only after Part A has been completed and safety of the doses has been established.

In Part A, the dose is planned to be escalated in cohorts at the pre-defined provisional dose levels; see Table 4.1.2: 1. Intermediate or lower dose levels, depending on the number of DLEs observed in the study, as long as they fulfil the EWOC criterion, may be investigated if agreed upon between Investigator and Sponsor. At the end of each treatment cohort, BI will convene a meeting with the SMC members. At the dose escalation meeting, all available systemic and ophthalmological safety data (See section 3.1 and 5.2.1) will be reviewed in

detail. Based on that and on the results of the updated BLRM, a decision on the next dose level to be tested is made.

In general, recruitment for Part A will be done successively for the dose groups, i.e. if the required number of subjects for one dose group is completed and this dose is considered safe based on (the BLRM model and the clinical course), the recruitment of the next higher dose group may be started. Therefore, the recruitment of subjects for the dose groups will neither be influenced by the trial personnel nor by any characteristics of the subjects, but only by temporal availability. Subjects from the Part A are not allowed to participate in Part B.

The highest dose (██████), if established as safe and tolerable during Part A will be used in Part B after Part A has been completed. If the highest dose (██████) is not considered safe and tolerable Part B will not commence. In Part B subjects will be randomized to receive either active IVT treatment or sham injection according to a randomization plan at visit 2 via Interactive Response Technology (IRT). 20 subjects will receive IVT treatment and 10 will receive sham injection.

The randomization procedure is described in Section [7.5](#).

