7.2 NULL AND ALTERNATIVE HYPOTHESES

No confirmatory testing is performed and hence no null and alternative hypotheses are defined. Any confidence intervals computed are to be interpreted in the perspective of the exploratory character of the study; i.e., confidence intervals are considered as interval estimates for effects. A discussion of the sample size is provided in Section [7.6](#).

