7.6 DETERMINATION OF SAMPLE SIZE

Part A:

No formal statistical power calculations to determine sample size were performed for this explorative study. A Bayesian logistic regression model (BLRM) was used for guiding the dose escalation process (see Section [3.1](#) for details). For the SRD part, a minimum of 3 subjects and a maximum of 18 subjects will be expected for this trial based on the number of dose levels/cohorts that are tested (for details regarding the BLRM assumptions refer to appendix [10.3](#)). Fewer subjects might be needed based on the recommendation of the SMC. However, the actual number of subjects will depend on the number of dose cohorts tested. Based on the simulation study to evaluate operating characteristics of the BLRM, about 15 evaluable subjects are expected to be treated in the dose escalation part for the model to have reasonable operating characteristics relating to its MFD recommendation.

Part B:

In the publication Samara et al. [[R17-3318](#)] estimates for FAZ means and standard deviations (SD) were derived. The worst case was for PDR subjects with mean deep FAZ of 0.766 mm². The standard deviation of FAZ ranged from 0.112 mm² to 0.3402 mm² for disease categories from control to PDR. It is assumed that intra-individual variability is much lower than the inter-individual SD from Samara et al. because of the high correlation of the baseline and the FAZ values after treatment. Taking into account the high correlation, a SD of FAZ of 0.1 mm² seems to be reasonable to be used in calculation of risk probabilities. With 20 subjects in the BI 765128 [REDACTED] arm and 10 subjects in the sham arm, there is a likelihood of 81.7% of observing a treatment effect larger than 6% (a reduction of 0.0462 mm²) and a likelihood of 10.2% of observing a treatment effect smaller than 4% (a reduction of 0.0308mm²) when the assumed mean treatment difference is 10%. Assuming a mean treatment difference of 0% there is a likelihood of 12.3% observing a treatment effect larger than 6% and a likelihood of 78.7% of observing a treatment effect smaller than 4%.

8. INFORMED CONSENT, TRIAL RECORDS, DATA PROTECTION, PUBLICATION POLICY, AND ADMINISTRATIVE STRUCTURE

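### SAP 7.5.2 promises two-sided 95% confidence intervals for FAZ area and BCVA, but the SAS code printed for the same model requests 90% intervals

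*SAP*

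**What the plan says.** SAP 7.5.2 defines the model-based analysis of the ophthalmological secondary endpoints in Part B: "Model-based analyses will be performed for all ophthalmological efficacy endpoints of the MD part that were defined as secondary endpoints, i.e. FAZ area and BCVA". The analysis is a repeated-measures mixed model on change from baseline in the study eye. Adjusted means by arm, and the difference between arms, are to be reported at each time point, and "in addition corresponding two-sided 95% confidence intervals and p-values will be presented".

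The section then prints PROC MIXED code, introduced by "The following SAS code can be used to fit the model". The statement that generates the adjusted means, their differences and their limits is "LSMEANS treat*visit/ DIFF CL ALPHA=0.1 SLICE=visit". The MODEL statement also contains `ALPHA=0.1`.

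Protocol 7.2 defines no hypotheses and treats confidence intervals as interval estimates of effects: "Any confidence intervals computed are to be interpreted in the perspective of the exploratory character of the study". It sets no confidence level, so the only stated level for these intervals is the 95% in SAP 7.5.2.

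**The concern.** In PROC MIXED the ALPHA option sets the confidence level of the limits requested by CL. The printed value therefore contradicts the sentence it is meant to implement.

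Part B has no formal tests, so a reader will judge the FAZ and BCVA effects largely from the estimates and their intervals. The level is part of what an interval means. If the code is run unchanged and the output is labelled as the text requires, intervals described as 95% would miss the true difference 10% of the time instead of 5%. FAZ effects at Visits 5, 6 and 7 and the BCVA effect at Visit 7 would look more precise than they are. The fast-track FAZ analysis (SAP 7.5.3) would probably inherit the problem if it uses the same program.

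The mismatch could also show in the tables. ALPHA does not change the p-values, so an interval labelled 95% could exclude zero beside a p-value between 0.05 and 0.10.

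**Working it through.** **Level requested against level promised**

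- Text: two-sided 95%, which needs ALPHA = 0.05.
- Code: 100 × (1 − 0.1) = 90%, two-sided.
- The stated 95% is not reproduced by the code.

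One possible reconciliation was tried. Each limit of a two-sided 90% interval is a one-sided 95% bound, since 1 − 0.1/2 = 0.95. The text says two-sided, so this does not bring the two together.

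**Search for an explanation**

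- SAP Section 4 (changes to the planned analysis) records the move to a repeated-measures mixed model and the dropping of LOCF. Its visible text records no change of confidence level.
- The SAP history table lists changes only to Sections 6.3 and 7 (two wording changes on p. 25) for version 2.0. It lists no correction to 7.5.2.
- The visible text of the protocol and SAP mentions no 90% interval for these endpoints.

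**Size, using the protocol's planning values for FAZ**

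Inputs:

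- Allocation (Protocol 4.1.3): "20 subjects will receive IVT treatment and 10 will receive sham injection".
- SD (Protocol 7.6): "a SD of FAZ of 0.1 mm² seems to be reasonable to be used in calculation of risk probabilities".
- Planned effect (Protocol 7.6): 10%. The protocol equates 6% with 0.0462 mm², so 10% is 0.0462 × 10/6 = 0.077 mm².
- Degrees of freedom: not given, so assumed. The simple two-group value is 20 + 10 − 2 = 28. A baseline covariate and missing visits would lower it, so a range down to 15 is shown.

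Standard error of the difference: SE = 0.1 × √(1/20 + 1/10) = 0.0387 mm².

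Half-width = t(1 − α/2, df) × SE:

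| df | t, 90% | t, 95% | Half-width 90% (mm²) | Half-width 95% (mm²) | Ratio 90/95 |
|---|---|---|---|---|---|
| 28 | 1.701 | 2.048 | 0.0659 | 0.0793 | 0.830 |
| 27 | 1.703 | 2.052 | 0.0660 | 0.0795 | 0.830 |
| 20 | 1.725 | 2.086 | 0.0668 | 0.0808 | 0.827 |
| 15 | 1.753 | 2.131 | 0.0679 | 0.0826 | 0.822 |
| Normal | 1.645 | 1.960 | 0.0637 | 0.0759 | 0.839 |

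The coded interval is 1 − 0.830 = 17% narrower than promised at 28 df. Put the other way, the promised interval is 20% to 22% wider for 28 down to 15 df. The SE cancels from the ratio, so the ratio does not depend on the SD and applies equally to BCVA.

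**What this does at the planned effect**

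Suppose the observed difference is exactly −0.077 mm², with 28 df:

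- 90%: −0.077 ± 0.0659 = (−0.143, −0.011), which excludes zero.
- 95%: −0.077 ± 0.0793 = (−0.156, +0.002), which includes zero.

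The t statistic is 0.077/0.0387 = 1.99, between 1.701 and 2.048, so the two-sided p-value lies between 0.05 and 0.10. The intervals disagree about zero at every df from 15 to 28. With normal quantiles the 95% half-width falls just below 0.077 mm² and both intervals exclude zero.

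**The case against.** The strongest reply is that the code is only an example. It is offered as usable, whereas the 95% level is something the plan says will be presented. On that reading the prose governs, a careful programmer corrects the option, and nothing goes wrong.

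The analysis is also exploratory. FAZ and BCVA are secondary endpoints with no key secondary among them, and the Part B primary endpoint is a descriptive count of subjects with drug-related adverse events. The sample-size reasoning in Protocol 7.6 uses thresholds for the observed effect (above 6%, below 4%), which ALPHA does not touch. Adjusted means, standard errors and p-values are also unchanged, so a correct p-value would stand beside each interval. The square-millimetre figures rest on a planning SD and assumed degrees of freedom.

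These points limit the consequence. No visible decision rule depends on the interval level, and no confirmatory error rate is at risk. Parts of both documents are blacked out, so the absence of a 90% level can be claimed only for the visible text. SAP 7.5.3 does not mention intervals, so the effect on the fast-track analysis is an inference.

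They do not remove the contradiction. The SAP does not say that text overrides code, and a reader cannot tell which level was meant. Code printed in a final SAP is likely to be copied.

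**Conclusion.** The concern holds. SAP 7.5.2 promises two-sided 95% intervals and prints code that produces two-sided 90% intervals for the same quantities. Run as printed, the code gives intervals about 17% narrower than promised, with 10% rather than 5% non-coverage if the model is correct. This applies to both FAZ area and BCVA.

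The contradiction and the 90% level require no assumption. The FAZ half-widths of 0.066 and 0.079 mm² assume an SD of 0.1 mm², a 20:10 split and 28 degrees of freedom. They illustrate the size and do not predict the trial's results. The practical harm depends on the code being used unedited and its output labelled 95%.

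**What to change.** Set `ALPHA=0.05` in both the MODEL and the LSMEANS statements, so that the code delivers the level the text specifies. If 90% intervals are intended, change the sentence in SAP 7.5.2 and every table and figure label to 90%, and give the reason.

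Settle this before unmasked efficacy results are seen, because a level chosen afterwards could look data-driven. The fast-track FAZ outputs should use the same level.

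The cost is two option values in the code, or a short change of text and labels. No data collection, estimate or p-value changes. With the 95% option, intervals are about 20% wider than the printed code would give.
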